### **3.5 Informed Consent**

If eligible, the 24-hour-on-call study coordinator is notified to begin a culturally appropriate consent process. Written informed consent for study procedures is obtained from legal guardians of patients by each participating site in Spanish. Verbal assent of the patient is also sought by ICU discharge if the patient is capable. Enrolled participants at the control sites consent to data collection from their medical records. Enrolled participants at the intervention sites consent to data collection and receive the intervention delivered by the trained ICU staff delivering their care. A patient or family/guardians can withdraw consent at any time. Should a patient or their family withdraw their consent, any previously collected data is removed from analysis and, if they are a patient at an intervention site, the PEGASUS clinical pathway is no longer used at the bedside, and they receive needed, usual care. The CIIC served as the regional coordinating center and storage warehouse for documentation. This protocol was performed according to the updated Declaration of Helsinki and all patients provided informed consent per local protocols for trial participation.

### **3.6 Risks**

There are minimal risks associated with the proposed study. The main risk for participants is loss of confidentiality, which will be protected as described in Chapter 8. Anticipated and unanticipated health risks will be reviewed and assessed as described in Chapter 5. There are no provisions for post-trial care.

[figure not shown]
### **3.7 Sample Size and Power**

A sample size of 432 participants is targeted for the planned parallel cluster study, which would have 80% power to detect a 18.7% higher ICU TBI guideline adherence rate with program implementation at the site level, with a two-sided alpha of 5%, and an intraclass coefficient of 0.05. Calculations included 58.6% guideline adherence rate estimate based on prior pilot work in Argentina and assumed no change in adherence rate at control sites. The study will not be sufficiently powered for secondary outcomes of patient mortality, discharge outcomes, or three-month follow-up outcomes.

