### 3.1 Study Design

This study is an open-label, multicenter, phase 3, superiority, pragmatic, parallel cluster randomized controlled trial (RCT) including 16 South American hospitals to provide usual care (n=8 sites) or the PEGASUS intervention (n=8 sites). This final design resulted after two iterations: the first iteration was a parallel cluster RCT with twelve sites (6 intervention, 6 control). In response to site requests for receiving the PEGASUS Pathway intervention, a stepped wedge design was developed and approved by the sponsor. However, the final study design was again updated in August 2020 after approvals from site PIs and sponsor from a stepped-wedge design due back to a parallel cluster RCT with sixteen sites (8 intervention, 8 control) due to COVID-19 pandemic challenges.

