### 3.3 Site Randomization Plan

Sixteen study sites were recruited by CIIC based on willingness to participate and annual severe TBI admissions. Sites were added after the original proposal to increase the potential patient recruitment population. All sites receive compensation for data submission. Prior to randomization on July 13, 2020, three sites who had no or one enrolled patient during ten months of baseline usual care data collection were removed from the pool. The remaining sixteen sites participating were ranked by median monthly baseline enrollment, number of zero recruiting months, and total number of recruited patients and divided into four groups (Group A=highest enrollment group, Group D=lowest enrollment group). The study statistician performed computer block randomization within each group to assign to control and intervention arms at a 1:1 ratio. Participant assignment was dependent on the intervention or control arm assignment of the study hospital to which they were admitted.

Due to the nature of the intervention study team, site staff, and patients' families are aware of the site's arm assignment.

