### **3.8 Recruitment, Retention & Follow-up**

Recruitment is limited to eligible patients admitted and consented at study sites. Based on baseline recruitment levels, the target sample size of 432 is feasible with about 9 participants per site per year. This is an in-patient intervention for the first 7 days of ICU care where intervention ICU staff are trained on intervention delivery as part of their patient care. Other data will be obtained from the health records. Follow-up data collection will be attempted at three months post-admission and can be completed in-person, via telephone, or from the health record. If unable to complete follow-up by four months, the participant will be designated lost-to-follow-up, but in-hospital data will be included. There is no incentive for participation offered to patients at any stage.

[figure not shown]

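### The stated 80% power reproduces only with 16 equal sites of 27 children; no allowance for unequal site size is stated, although the sites were ranked and grouped by enrolment

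*Protocol*

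**What the plan says.** Protocol section 3.7 sets the target: "A sample size of 432 participants is targeted for the planned parallel cluster study". It claims a design "which would have 80% power to detect a 18.7% higher ICU TBI guideline adherence rate with program implementation at the site level". The error rate and the clustering allowance follow in the same sentence: "with a two-sided alpha of 5%, and an intraclass coefficient of 0.05". The control rate is given as follows: "Calculations included 58.6% guideline adherence rate estimate based on prior pilot work in Argentina". The calculation also "assumed no change in adherence rate at control sites".

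Section 3.1 fixes the clusters, "including 16 South American hospitals to provide usual care (n=8 sites) or the PEGASUS intervention (n=8 sites". Section 3.8 gives only an average recruitment rate: "the target sample size of 432 is feasible with about 9 participants per site per year". Chapter 4 sets the intervention period at October 2020 to September 2023, which is three years.

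Section 3.3 describes how the sites were prepared for randomisation. Three sites with at most one enrolled child over ten baseline months were dropped. The remaining sixteen were ranked on three measures of baseline enrolment and "divided into four groups (Group A=highest enrollment group, Group D=lowest enrollment group"). Randomisation was 1:1 within each group. No site counts are reported.

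The SAP (Methods, item 2) plans a mixed-effects Poisson model with robust variance and clustering by site. The SAP's outcome definition makes adherence a fraction for each child: indicators met over indicators relevant.

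**The concern.** In a cluster trial with a fixed total sample and a positive ICC, unequal clusters carry less information than equal ones. The plan shows that its sites recruit at different rates, since it graded them on that basis, but the power statement contains nothing that reflects it. Randomising within enrolment groups balances site size between the arms. It does not remove the variation in size within each arm, and that variation is what raises the design effect.

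Section 3.7 is the protocol's only power statement, so a null result would be judged against its 80%. If the calculation assumed equal sites and the sites are not equal, that benchmark is too favourable on the plan's own method.

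**Working it through.** **Inputs from the documents.** N = 432, so 216 per arm; 8 sites per arm; control rate 0.586; difference 18.7; ICC 0.05; two-sided alpha 5%. Mean site size is 9 × 3 = 27, and 27 × 16 = 432.

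**Reading of the 18.7%.** It is taken as percentage points, 0.586 to 0.773. Read as a relative increase it would give 0.586 × 1.187 = 0.696 and power of about 35%, so only the absolute reading fits the stated 80%.

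**Step 1: reproduce the plan's figure with equal sites.**

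- Design effect: 1 + (27 − 1) × 0.05 = 2.30
- Effective children per arm: 216 / 2.30 = 93.9
- Standard error (unpooled): √[(0.586 × 0.414 + 0.773 × 0.227) / 93.9] = √[(0.2426 + 0.1755) / 93.9] = 0.0667
- Power: Φ(0.187 / 0.0667 − 1.96) = 80.0%
- Detectable difference at 80% power: 18.69 points

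Both stated figures are recovered, with nothing left over. A pooled-variance version gives 78.9%.

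**Step 2: allow for unequal sites, every child weighted equally.** The design effect becomes 1 + [(1 + CV²) × 27 − 1] × 0.05. The CV is an assumption, so a range is shown.

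| CV of site size (assumed) | Design effect | Effective n per arm | Loss of effective n | Power for 18.7 points | Detectable difference at 80% |
|---|---|---|---|---|---|
| 0 | 2.30 | 93.9 | 0% | 80.0% | 18.7 |
| 0.2 | 2.35 | 91.8 | 2% | 79.1% | 18.9 |
| 0.33 | 2.45 | 88.3 | 6% | 77.6% | 19.2 |
| 0.5 | 2.64 | 81.9 | 13% | 74.5% | 19.9 |
| 0.6 | 2.79 | 77.5 | 17% | 72.1% | 20.3 |
| 0.8 | 3.16 | 68.3 | 27% | 66.6% | 21.5 |

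**Step 3: efficient weighting.** Effective n per arm is the sum over sites of m / [1 + (m − 1) × 0.05], where m is the site size. The illustrative sizes below have two sites per group in each arm and keep the mean at 27.

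- Sizes 40/30/22/16 (CV 0.33): 2 × (13.56 + 12.24 + 10.73 + 9.14) = 91.4, power 78.9%.
- Sizes 55/28/16/9 (CV 0.65): 2 × (14.86 + 11.92 + 9.14 + 6.43) = 84.7, design effect 216 / 84.7 = 2.55, power 75.9%.

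**Step 4: a reference point for the smallest plausible CV.** If all sites shared one true recruitment rate and counts were Poisson (an assumption), chance alone would give a three-year CV of 1/√27 = 0.19 and power of about 79.2%. Real differences between groups A and D would add to that.

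**The case against.** A reader might infer from the table that, on the protocol's own inputs, the power is 67–78%, or that the trial cannot deliver 80%. The documents do not support either statement, for four reasons.

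- **The CV is not in the documents.** A ranking from A to D shows that sites differ, not by how much. Dropping three very low recruiters also trimmed the lower tail. At CV 0.2 the loss is under one point, so modest departures from 27 per site hardly matter. This stands: every figure below 80% is conditional on an assumed CV.
- **The low end is pessimistic.** The 67% needs both CV 0.8 and equal weight for every child. The SAP plans a mixed-effects model, and efficient weighting loses less. This also stands, and is why both weightings are shown.
- **The outcome is not a yes/no event.** It is a fraction for each child, and its SD is not given. The plan's binomial variance corresponds to an SD of about 0.457. Under a normal approximation with an assumed SD of 0.39, power would be about 80% even at CV 0.8 with equal weighting; with a smaller SD it would be higher. Absolute power could therefore exceed the figures shown. That does not repair the stated calculation, whose figures match a two-proportion, equal-cluster formula. For a given CV and weighting, the proportional loss of effective sample size is the same whatever the SD.
- **A raw baseline CV would overstate the problem.** Ten months at about 9 a year is 9 × 10/12 = 7.5 children per site, for which Poisson chance alone gives a CV of 1/√7.5 = 0.37, against 0.19 for 27. This stands and shapes the fix.

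**Conclusion.** The arithmetic in section 3.7 is right for 16 equal sites of 27 and leaves no margin. The protocol shows that the sites were known to differ in enrolment, and it states no allowance for that. With the other inputs held fixed, any inequality lowers the power, so on the plan's own method the 80% is overstated.

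The direction is certain; the size is not. For an assumed CV of 0.2 to 0.8 with equal weighting, power is about 79% down to 67%, and the detectable difference rises from about 18.9 to 21.5 points. Efficient weighting gives about 79% at CV 0.33 and 76% at CV 0.65. All these figures keep the plan's yes/no variance, its ICC of 0.05 and a normal reference.

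The finding concerns the planning statement. It does not show that the trial is underpowered for the adherence score as the SAP defines it, because the SD of that score is not given.

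**What to change.** Recompute section 3.7 with a design effect for unequal clusters, and state the assumed CV and the weighting. Then restate either the power for 18.7 points or the difference detectable with 80% power.

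Estimate the CV from the baseline counts of the sixteen randomised sites, corrected for the shorter counting period. One way, assuming Poisson counts, is to subtract 1/(mean baseline count) from the squared baseline CV and add 1/27. As an illustration, an observed CV of 0.6 at a mean of 7.5 becomes √(0.36 − 0.133 + 0.037) = 0.51.

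The cost is one recalculation and probably a slightly less favourable stated figure. The counts were already used for the ranking before randomisation in July 2020. Do not add patients; neither the design nor the analysis needs to change.

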## 4.3 TBI Guideline Adaptations

During the baseline study period, the full study team, including the sites provided input on TBI guidelines in the local context and impact on the relevant indicators in the guideline adherence calculation scorecard.

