#### 8.4 Data Collection Timeline

Baseline data collection will occur at all participating sites from September 2019-September 2020. From October 2020-September 2023, intervention sites will collect additional data associated with the intervention implementation. The Data Collection Timeline below shows the data types collected (leftmost column) and the intervals of repeated measures.

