**Questions of interest:**

- 1) Does PEGASUS implementation improve guideline adherence?
- 2) Are there any imbalances between the study arms that need to be addressed?

**Study Design:** 2-arm parallel cluster RCT

**Study population:** Pediatric (<18) ICU patients with severe TBI at 16 sites

**Exposure variable(s):** Study Arm (binary)

**Outcome variable(s):** (1) TBI guideline adherence

*"The main outcome is TBI guideline adherence during first 3 days ICU stay, calculated via our previously developed TBI guideline adherence scorecard. Using patient charts, we measure presence or absence of adherence to the indicators and capture time since injury for any observed indicators, including the main protective KPIs (ventilation, nutrition, CPP). Patient guideline adherence is defined as the sum of indicators to which care was adhered divided by the number of relevant adherence indicators for a given patient. Mean adherence scores are calculated for each site individually and across all sites."*

Describe:

- (2) Extracranial injuries
- (3) Discharge GOS
- (4) Discharge survival
- (5) 3-month GOSE-Peds
- (6) 3-month mortality
- (7) KPIs?

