**Methods:**

1. Descriptive statistics for all measures at the facility level, within treatment and control arms. Potential differences in patient (age, sex, race/ethnicity) and injury characteristics will be examined using bivariate analyses by center using  $\chi^2$  tests (categorical) and t-tests (continuous).
2. ITT analysis: multi-level mixed effects Poisson regression with robust variance estimation and clustering by site to estimate the relative risk of PEGASUS implementation on TBI guideline adherence and stratified by extracranial injury, as described in Zou, et al.  
Per protocol: As with ITT, but potentially including implementation dose/fidelity as covariate and interaction with intervention.
3. Secondary analyses (Following ITT for primary analysis): Poisson regression with robust variance estimation and clustering by site to estimate separately the relative likelihood of program implementation on these outcomes: 1) in-hospital mortality; and 2) GOSE-Peds at 3 months post TBI, analyzing GOS score as a dichotomous measure (minor-moderate impairment vs major impairment-vegetative state and death).  
Multivariable Cox regression model to examine the marginal effect of PEGASUS on mortality during the 3 months post discharge, averaged over all centers.
4. Sensitivity analyses: repeated analysis on ICP monitoring patients
5. Subgroups: COVID effect and geographic effect

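### The primary test clusters on only 16 sites with no stated small-sample correction, so the planned 5% error rate is not secured; separately, the 18.7% effect is unlabelled and has no SD

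*Protocol*

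**What the plan says.** **Primary analysis.** The SAP (Methods, item 2) plans "multi-level mixed effects Poisson regression with robust variance estimation and clustering by site to estimate the relative risk of PEGASUS implementation", and refers to a cited methods paper for the technique. Protocol 3.1 gives 16 hospitals, 8 per arm. Protocol 3.3 says that, before being divided into four groups for randomisation, sites were "ranked by median monthly baseline enrollment, number of zero recruiting months, and total number of recruited patients". No site sizes are given.

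**Primary outcome.** The SAP (Outcome variables) states: "Patient guideline adherence is defined as the sum of indicators to which care was adhered divided by the number of relevant adherence indicators". It adds: "Mean adherence scores are calculated for each site individually and across all sites". Protocol 4.3 likewise refers to "the relevant indicators in the guideline adherence calculation scorecard". Nowhere is the score cut into yes/no.

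**Power.** Protocol 3.7 claims "80% power to detect a 18.7% higher ICU TBI guideline adherence rate with program implementation at the site level" for 432 patients, with two-sided alpha 5%, an intraclass coefficient (ICC) of 0.05 and a control rate of 58.6%. It names no SD and no test, and does not label the 18.7%. Protocol 3.8 says "the target sample size of 432 is feasible with about 9 participants per site per year".

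**The concern.** A site-clustered robust variance is justified when there are many clusters. With 8 per arm it is biased downwards, because each site's residual is measured from an arm mean that the site itself helped to set. It is also noisy, so its ratio to the estimate has heavier tails than the normal. Both effects produce too many false positives, and unequal site sizes make them worse. If the cutoff and variance formula are chosen after the data are seen, that choice could decide whether the primary result is significant.

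The power statement raises a smaller question. It speaks of an adherence rate, while the analysis uses a per-patient fraction whose spread is not given. A reader cannot tell what difference the trial is designed to detect on its own primary outcome.

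**Working it through.** **Inputs.** 16 sites, 8 per arm (Protocol 3.1). 9 patients per site per year (3.8) × 3 years (October 2020–September 2023, Chapter 4) = 27 per site; 27 × 16 = 432, or 216 per arm. ICC 0.05, alpha 5% two-sided, control 58.6% (3.7). Design effect = 1 + 26 × 0.05 = 2.3. The score SD and the site-size CV are not in the documents; the values below are assumptions.

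**1. The plan's own figure.** Take 18.7% as absolute and the outcome as yes/no: 58.6% vs 77.3%.

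- SE = √[(0.586 × 0.414 + 0.773 × 0.227) × 2.3/216] = 0.0667
- 0.187/0.0667 = 2.803; power = Φ(2.803 − 1.960) = 80.03%

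This reproduces the stated 80%. The match is not unique. Take 18.7% as relative: 0.586 × 1.187 = 0.6956, a difference of 0.1096. For a fractional score, SE = SD × √(2 × 2.3/216) = SD × 0.1459. Power is 80% at SD 0.268 (normal reference) or 0.249 (t, 14 df). The relative reading with a yes/no outcome gives only 35%.

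**2. Power for the fractional score** (ICC 0.05, equal sites, t with 14 df):

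| Assumed SD | Absolute, 18.7 points | Relative, 11.0 points | Difference detectable at 80% (3.013 × SE) |
|---|---|---|---|
| 0.20 | >99.9% | 93.7% | 8.8 points |
| 0.25 | 99.7% | 79.8% | 11.0 points |
| 0.30 | 97.7% | 64.4% | 13.2 points |

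The ICC also matters. On the absolute reading, power falls below 80% if the ICC exceeds about 0.14 (SD 0.30), 0.22 (SD 0.25) or 0.36 (SD 0.20).

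**3. Type I error with a 1.96 cutoff, equal sites.**

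- Heavy tails alone: 2 × P(t₁₄ > 1.960) = 7.0%.
- Adding the downward bias: with 8 sites per arm the plain sandwich variance is on average 7/8 of the correct one. A common software factor of 16/15 brings it to 7/8 × 16/15 = 14/15. The effective cutoff is 1.960 × √(14/15) = 1.894, and 2 × P(t₁₄ > 1.894) = 7.9%.
- Without the 16/15 factor: 1.960 × √(7/8) = 1.833, giving 8.8%.

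**4. Simulation with no true effect.** Fractional scores with mean 0.586 and ICC 0.05; 432 patients; four size groups of four sites randomised 2:2; arm-only log-link Poisson with site-clustered variance × 16/15; 20,000 runs per setting (Monte Carlo SE about 0.2 points). Ranges cover repeated independent runs.

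| Test | Equal sites | CV 0.5 | CV 0.7 |
|---|---|---|---|
| Robust variance, 1.96 | 7.6–8.0% | 9.2–9.5% | 10.6–10.9% |
| Robust variance, t with 14 df | 5.6% | 6.9–7.0% | 8.1–8.3% |
| Kauermann-Carroll variance, t with 14 df | 4.8–5.1% | 5.5–5.9% | 6.4–6.8% |
| t test on 16 site means, 14 df | 4.7–5.1% | 4.7–5.1% | 4.7–5.1% |

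The planned site random intercept does not remove the problem if the fraction itself is the Poisson response. At SD 0.25 the variance of a site mean is 0.25² × 2.3/27 = 0.0053, against 0.586/27 = 0.0217 implied by the Poisson model. The intercept variance was therefore estimated at zero in at least 99.9% of runs, and the robust variance carries the clustering.

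**The case against.** The SAP does not prescribe 1.96. It is silent, and the methods paper it cites, which cannot be consulted here, may address small samples. That stands: the excess error is conditional on the default reference being used. The point is that neither document fixes the choice in its own text.

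The simulation is simpler than the plan. It has no covariates and does not examine a count-with-offset form. The CVs are assumed, and Protocol 3.3 removed three sites with at most one patient before randomisation, which limits extreme imbalance. This also stands, so the 9–11% is a range under assumptions. The equal-site figure needs no CV assumption, and direct calculation gives nearly the same value.

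Two stronger readings of the power statement are tempting. A reader might infer that the trial is underpowered, because the yes/no calculation falls to 74.1% with 14 df. That is not supported: the primary outcome is not yes/no, and a fractional score with the same means cannot have a larger variance. A reader might instead infer that the stated power is safely conservative. That holds only on the absolute reading and near the stated ICC. Because the SAP estimates a relative risk, the relative reading is a fair one, and power there is 64.4% at an assumed SD of 0.30. Nor is there an arithmetic error, since the stated 80% can be reproduced.

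**Conclusion.** The main point holds as a specification gap in the primary test. With 16 sites, a robust variance and the usual normal reference, two-sided type I error is about 8% with equal sites and about 9–11% at assumed CVs of 0.5–0.7, against 5%. This rests on an arm-only model, ICC 0.05 and a 1.96 cutoff that the SAP neither states nor rules out. It should be fixed, because the remedy is cheap and the choice can decide the primary conclusion.

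The power point is minor. The 18.7% is unlabelled and the score has no SD. The yes/no basis is an inference from a close numerical match, not something the protocol states. The documents do not settle whether the stated power is too high or too low for the planned analysis.

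**What to change.** **SAP, Methods item 2.** State that the primary test and interval use:

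- a t reference with between-site degrees of freedom: 16 − 2 = 14 for an arm-only model, 14 − 3 = 11 if the four enrolment groups are included, and fewer with site-level covariates;
- a leverage-corrected robust variance, such as Kauermann-Carroll.

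Pre-specify a t test on the 16 site means as a companion analysis. The SAP already calculates these means. Because the corrected robust test still runs at about 6.4% at CV 0.7, state in advance the degree of site-size inequality beyond which the site-means test is relied on. That test weights sites equally and gives a difference in means, not a relative risk, and the SAP should say so.

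**Protocol 3.7.** Keep 432. Say whether 18.7% is absolute (58.6% to 77.3%) or relative (58.6% to 69.6%). Restate the power or detectable difference for the fractional score, using the same t reference and the SD, ICC and site-size variation from the baseline patients; Protocol 8.4 says "Baseline data collection will occur at all participating sites from September 2019-September 2020". Do not publish 74% as the trial's power.

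**Cost.** A short SAP addition and one recalculated protocol paragraph, with no extra patients. With equal sites, the primary interval widens by 2.145/1.960 = 1.094, about 9%, from the t reference alone. Adding Kauermann-Carroll multiplies this by √(8/7)/√(16/15) = 1.035, giving about 13%.
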